HAART	Highly Active Antiretroviral Therapy
HEENT	Head, ears, eyes, nose, and throat
HIPAA	Health Insurance Portability and Accountability Act
HIV	Human Immunodeficiency Virus
ICF	Informed Consent Form
ICH	International Conference on Harmonisation
IgE	Immunoglobulin E
IM	Intramuscular
IRB	Institutional Review Board
IRT	Item Response Theory
mg	Milligram
ml	Milliliter
N	Number (typically refers to subjects)

NIAID	National Institute of Allergy and Infectious Diseases, NIH, DHHS
NIH	National Institutes of Health
NPV	Negative Predictive Value
PCN	Penicillin
PD	Protocol Deviation
PE	Physical Exam
PN	Participant Number
PST Group	Penicillin Skin Test Group
SAP	Statistical Analysis Plan
SI	Site Investigator
STD	Sexually Transmitted Disease
U/ml	Units per milliliter
UK	United Kingdom
UPIRISO	Unanticipated problems involving risks to subjects or others
US	United States
USP	United States Pharmacopeia

PROTOCOL SUMMARY

Title:	Validate an Easy to Administer Algorithm to Define Penicillin (B-lactam) Allergy Status in STD Outpatients
Population:	Approximately 5000 patients coming for care at Sexually Transmitted Disease (STD) clinics, emergency departments or ambulatory clinics will be screened to achieve 1000 evaluable subjects.
Number of Sites:	Four
Study Duration:	Approximately 27 months from implementation of field activity through closure and analysis.
Participant Duration:	One or two-visit study: screening for eligible subjects with history of penicillin (PCN) (B-lactam) allergy; enrollment; same day administration of PCN (B-lactam) allergy history screening questionnaire. Each site will perform two allergy validation methods using a sequential enrollment design. Method 1: skin testing of subjects with low-risk history; one-step oral challenge of subjects with negative skin tests. Method 2: direct two-step oral challenge of subjects with low-risk history. If subject cannot stay to complete all study procedures, skin test and/or oral challenge may be completed another day.
Objectives:	Primary: 
Validate an algorithm which incorporates a PCN (B-lactam) allergy history screening questionnaire followed by an allergy validation intervention — 1) skin testing and oral challenge or 2) direct two-step oral challenge — to produce a short standardized post-study questionnaire (4-6 questions) for use in ambulatory STD settings.Determine how many subjects who report PCN (B-lactam) allergy can be treated with PCN or B-lactam drugs. Secondary: 
Assess subject and provider acceptability of a PCN (B-lactam) allergy testing algorithm.

[figure not shown]
- Determine the feasibility of implementing PCN skin testing followed by oral challenge for those who skin test negative or direct two-step oral challenge in an ambulatory STD setting.

**Estimated Time to
Complete Enrollment:**

Approximately **14-16 months** for screening and enrollment.

SCHEMATIC OF STUDY DESIGN

[figure not shown]
Total N: Approximately 5,000 patients screened to achieve 1,000 evaluable subjects.

SCHEMATIC OF PROVIDER FEASIBILITY SUB STUDY DESIGN

Total N: Up to 150 clinicians from the five participating clinics.

Pre-Study
Implementation
AND
End of Study

2 BACKGROUND INFORMATION AND SCIENTIFIC RATIONALE

2.1 Background Information

Penicillin and cephalosporins both belong to the B-lactam class of antibiotics. These antibiotics play a critical role in treatment of STDs such as syphilis and gonorrhea. Current first line therapy for syphilis is intramuscular benzathine penicillin and for gonorrhea it is the third-generation cephalosporin ceftriaxone. Although there is only limited cross reactivity between PCN allergy and third generation cephalosporins such as ceftriaxone, many clinical settings will not administer this drug to patients reporting PCN (B-lactam) allergy. Second line treatments for gonorrhea are not as effective, especially at non-genital sites of exposure.

There are no first line therapy options for syphilis patients who have B-lactam allergy. These patients are usually treated with doxycycline for a prolonged course. Treatment options for anorectal and pharyngeal gonorrhea are even more limited.

Up to 20% of patients seeking medical care report a history of PCN or B-lactam allergy.^{1,2} However, when these patients are tested for allergy with formal skin testing, only a small minority of them are found to be allergic with immunoglobulin E (IgE) mediated hypersensitivity.^{1,2} The term allergy is often conflated with any type of drug intolerance or intolerance history.³ Most providers will not routinely administer B-lactam drugs to patients who report PCN allergy.^{1,2} Over-reported penicillin allergy can adversely impact care in settings where STD care is provided.

It has been nearly three decades since PCN allergy was evaluated in the STD clinic setting by Gadde and coauthors⁴ who studied this issue in Baltimore in the early 1990s. Of the 776 patients (among 5063 screened) who reported a PCN allergy history, only 55 (7.1%) had skin test reactivity, compared to 1.7% of 4287 with no allergy history. Higher skin reactivity rates were found in patients who reported anaphylaxis (17%) or urticaria (12%). Atopy rates were similar in both skin test positive and negative groups and was not useful as a predictive marker. No similar contemporary data are available.

More recently, the crisis of multiple drug resistant organisms and increased appreciation of PCN (B-lactam) allergy overdiagnosis has raised awareness of the issue. Overdiagnosis of PCN (B-lactam) allergy has been increasingly seen as a critical policy issue⁵ related to antibiotic stewardship and health care costs.^{6,7} Because patients with PCN (B-lactam) allergy are often administered second line drugs that are more broad spectrum and less efficacious, there are clear associations between patients with reported PCN (B-lactam) allergy and increased rates of *Clostridium difficile* and methicillin-resistant *Staphylococcus aureus*,⁸ surgical site infection for elective procedures,⁹ overall length of stay and overall health care costs in a large Kaiser managed care population¹⁰ and United Kingdom (UK) teaching hospitals.¹¹

Although the impact of PCN (B-lactam) allergy on patient outcomes is substantial, in practice, few patients with reported allergy, when evaluated, have confirmed allergy.^{5,7,10,12,13} Furthermore, anaphylaxis to penicillin and cephalosporins is rare. Macy¹³ recently reviewed all penicillin and B-lactam use between 2009-2017 in the Kaiser Permanente Southern California system. Of 6,144,422 unique health plan members, 2,114,406 members received 4,558,1965 courses of oral PCNs, and 192,925 persons received 285,984 parenteral PCN courses. Of these, there were 32,133 new PCN allergy reports (0.66%) within 30 days. Anaphylaxis occurred in only 22 patients (1 in 207,191) with oral B-lactam exposures; there were only 2 severe cutaneous reactions, both of whom also had had exposure to cotrimoxazole. The clinical impression is that anaphylaxis is less common now than in the early B-lactam era, which may be due to purer preparations of drug, less parenteral administration and increased use of later generation B-lactams.^{1,2}

The most reliable way to objectively define the presence of PCN allergy is by skin testing. Skin testing for PCN allergy can be easily performed as an outpatient with commercially available reagents (PRE-PEN® AllerQuest LLC, Plainville CT) and commercially available penicillin G. However, allergy referral and testing are typically either not available or difficult to access in most busy clinical settings, both inpatient and outpatient. Furthermore, the standard of care for STDs requires that patients be treated at the time of diagnosis or as soon as possible after exposure, which makes referral for allergy testing impractical. Therefore, patients who are being treated for syphilis or gonorrhea or contact exposure and who also report B-lactam allergy, are often treated with second line, and potentially less effective, therapy options, even though >90% may not have true allergy.

In clinical practice, because of the increasing demand for PCN (B-lactam) allergy evaluation and the lack of available allergist resources, various models to extend PCN skin testing have developed in both inpatient and outpatient settings. These models include testing and evaluation performed by hospitalists,¹⁴ infectious diseases physicians,¹⁵ pharmacists¹⁶ and as part of routine pre-operative evaluations.¹²

The currently approved PRE-PEN® kits contain only the PCN major determinant (penicilloylpolylysine) and one minor determinant. Since some patients may react only to the PCN minor determinants, which may occur in up to a quarter of true allergic cases, the current kits are estimated to have a sensitivity of about 75%.¹⁷ Skin testing itself is safe, even in sensitized subjects. In a large 2018 review, Adkinson¹⁷ summarized 54 studies, which included 19,259 patients, and found a reported adverse event (AE) rate of 0.16%, none of which were serious or life threatening.

Therefore, absent approval of the newer comprehensive kit, there is consensus within the allergy community that to define an individual as PCN-allergy negative, skin testing should be supplemented by a single dose oral challenge (usually with amoxicillin 250 mg).

Because of the increased appreciation of the overreporting of PCN allergy, investigators have developed PCN allergy evaluation approaches that bypass the skin testing step¹⁸ using risk

stratification criteria to identify patients with reported allergy who have a high negative probability of being truly reactive. Low risk was identified as having GI reaction only (nausea, vomiting), having family history without a direct personal history, having had a history of taking a B-lactam drug and having an ill-defined allergic reaction in the distant past (>5 years).

Higher-risk groups were described as having the following symptoms within a year: hives or other pruritic rash, blister or bullous skin eruption after B-lactams, or IgE related symptoms (swelling/angioedema, syncope, dyspnea/wheezing or hypotension).

The smaller clinical trials found that if patients had low-risk symptoms only (i.e., no higher-risk symptoms), then direct oral challenge was safe. Furthermore, on an institutional basis, these protocols are being adopted in practice settings, and have been implemented in a number of large health systems such as Kaiser Permanente in California and Partners Health in Massachusetts. There have also been smaller reports of similar risk stratification being used to optimize pre-operative prophylaxis.

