If there is a positive reaction to PRE-PEN® and/or Penicillin G during the prick test or the intradermal test, the participant is ruled out of the oral challenge with amoxicillin 250 mg. They will be counseled that their PCN allergy history was confirmed. Written documentation will be provided to the subject with instructions to share with their medical provider(s).

If the result of the intradermal test is ambiguous (equivocal), the intradermal test will be repeated with both reagents and the negative control in duplicate or, depending on each study clinic's procedures, the subject will be referred to a local allergy consultant or clinic. If the repeat intradermal test is positive or ambiguous or the initial reaction was uninterpretable, the participant will not proceed to the oral challenge and will be referred to an allergist for further evaluation.

Study staff will photograph the subject's arm to document the results of the skin test reactions using an iPad. No identifiers except a label containing the PN and a measuring guide will be included in the photograph. The images will be uploaded to the clinical database. Complete skin test responses (both prick and intradermal) will be recorded on the PCN skin test results CRF.

Occasionally, allergy skin tests can produce a severe, immediate allergic reaction. These are largely eliminated by doing the preliminary prick skin test. These can be treated with antihistamines, steroids or both. Infrequently, these symptoms this can require immediate medical treatment with epinephrine.

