7.1.2 Post-Skin Testing

- Subjects will be observed for 30 + 5 minutes and 60 + 5 minutes after skin testing. Assessment of elicited reactivity to PCN will include local skin reactions including erythema, induration and itching which will be evaluated both by self-report and physical exam. Systemic reactions are extremely rare.
- Subjects with positive skin tests will not progress to oral challenge step.

An impending generalized reaction to immediate hypersensitivity skin testing is unusual. If any acute reactions occur, they will be treated as necessary and reported to the IRB and DMID as required.

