8.2 Sample Size Considerations

The sample size for this study was selected to have adequate study power to conclude a high NPV of the PCN (B-lactam) allergy history screening questionnaire in ruling out the presence of true PCN (B-lactam) allergy. To address the objective properly, we applied Steinberg's et al.³² approach to obtain the minimal sample size needed to achieve a lower 95% confidence bound for NPV that exceeds the NPV with a useless test at a fixed level of significance with a given study power. Based on this approach, the sample size calculation depends on the prevalence of PCN allergy in the population and among observed study participants and the sensitivity and specificity of the PCN allergy diagnostic kit (PRE-PEN®). To target at least 85% power at 5% of significant level, the listed sample sizes (see table) provide lower 95% confidence bounds for NPV under the following various assumptions:

- The true population prevalence with PCN allergy: 1%, 3%, 5%
- The observed % of PCN allergy in this study: 1%, 3%, 5%
- The PCN allergy diagnostic kit with sensitivity at least 85% and specificity 95%
- 5% of participants who report a PCN allergy history will have a high-risk allergy history and therefore will not proceed to skin testing.

Population prevalence of PCN allergy	Observed % of PCN allergy in study	Estimated NPV	The lower 95% confidence bound for NPV						
			99.0%	98.4%	97.9%	97.5%	97.3%	97.0%	95.0%
1%	1%	99.84%	1259	796	635	556	526	488	351
	3%	99.51%	420	265	212	185	175	163	117
	5%	99.18%	252	159	127	111	105	98	70
3%	1%	99.84%	8119	2964	1958	1559	1421	1259	759
	3%	99.51%	2707	988	653	520	474	420	253
	5%	99.18%	1624	593	392	312	284	252	152
5%	1%	99.84%	113000	9519	4770	3378	2950	2483	1259
	3%	99.51%	37547	3174	1590	1126	984	828	420

	5%	99.18%	22533	1905	954	676	590	497	252
--	----	--------	-------	------	-----	-----	-----	-----	-----

For example, with 3% PCN allergy prevalence in population and among observed study participants, the NPV for a useless test is 97%. A useful PCN (B-lactam) allergy history screening questionnaire should have the lower 95% confidence bound for NPV greater than 97%. Based on the list a minimum sample size of 988 subjects who reported to have PCN allergy history would provide an estimated NPV = 99.51% with 85% power to conclude that the NPV of the study allergy history screening questionnaire is least 98.4% at 5% significant level.

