7.3 Analysis of Primary Objective

The primary analysis will be performed on the Treated population and Per Protocol population. Estimates with corresponding exact (Clopper-Pearson) 95% confidence intervals for the following measures will be provided:

- The prevalence of PCN reactivity validated either by skin test or by direct oral challenge among those participants who report a history of PCN (B lactam) allergy and who have low-risk histories.
- The NPV on true PCN (B-lactam) allergy of the algorithm / PCN (B-lactam) allergy history screening questionnaire performance in the Treated population.

The NPV for each low-risk allergy item listed on the questionnaire will be estimated and will be compared with the prevalence of PCN reactivity using exact test of binomial proportion. The p-values will be adjusted with Benjamini-Hochberg procedure.

To construct a short standardized post-study questionnaire (4-6 questions) from the PCN (B-lactam) allergy history screening questionnaire, we will first use the item-characteristic curve from Item Response Theory (IRT) to evaluate each question item's discrimination ability of true PCN (B-lactam) allergy and use variable importance evaluation functions to indicate which questions are most useful for predicting the true PCN (B-lactam) allergy. Based on the results of IRT and variable importance analyses, we will then apply machine learning approaches such as random forest (Svetnik et al., 2003) via R package caret, to select a short post-study questionnaire that has the highest NPV among those possible short questionnaires with 4-6 selected questions.

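### Skin-test positives count as true allergy without challenge, and neither the sample size nor SAP 7.3 allows for false positives, so the stated power for the 98.4% NPV bound is not secured

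*Protocol*

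**What the plan says.** Protocol 2.1 regards skin testing as the best objective standard: "The most reliable way to objectively define the presence of PCN allergy is by skin testing". Under Protocol 6.2, after a positive prick or intradermal test "the participant is ruled out of the oral challenge with amoxicillin 250 mg", and of such subjects it says: "They will be counseled that their PCN allergy history was confirmed". Protocol 7.1.2 repeats the rule: "Subjects with positive skin tests will not progress to oral challenge step". Skin-test negatives go on to a 250 mg challenge (Protocol 6.2.1). The direct oral challenge (DOC) group has no skin test (Protocol 4.1).

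The primary prevalence outcome counts reactivity shown by skin test or by direct challenge (Protocol 8.1.1, 8.4.1; SAP 7.3). The other primary measure in SAP 7.3 is "The NPV on true PCN (B-lactam) allergy of the algorithm / PCN (B-lactam) allergy history screening questionnaire performance in the Treated population". SAP 7.3 specifies Clopper-Pearson intervals and no correction or sensitivity analysis for error in the reference test. The same allergy labels drive the choice of the 4-6 question form.

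Two figures in the documents bear on skin-test false positives. Protocol 8.2 and SAP 6 assume "The PCN allergy diagnostic kit with sensitivity at least 85% and specificity 95" per cent. Protocol 2.1 reports, among earlier STD-clinic patients with an allergy history, that "only 55 (7.1%) had skin test reactivity, compared to 1.7% of 4287 with no allergy history".

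**The concern.** The PST pathway corrects one kind of skin-test error and not the other. A false negative can be picked up at the oral challenge. A false positive stays in the data as a case of true allergy that the low-risk history failed to exclude.

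The target leaves little room for this. The trial wants to conclude an NPV of at least 98.4% from an expected 99.51%, so a few extra positives among some 950 tested subjects decide the result. A sound questionnaire could be reported as falling short because of its reference test. Positive labels unrelated to history would also blur the item discrimination and variable-importance results behind the short form, where events are few.

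**Working it through.** **Inputs.** Sensitivity 85%, specificity 95%, prevalence 3%, target bound 98.4%, power 85%, significance level 5%, high-risk share 5% (Protocol 8.2, SAP 6). Allocation 1:1 (Protocol 4.1). Two-sided 95% exact intervals (SAP 5, 7.3). Reactivity without an allergy history 1.7% (Protocol 2.1).

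**Step 1: reproduce the plan.** Expected NPV = Sp(1 − p) / [Sp(1 − p) + (1 − Se)p] = 0.95 × 0.97 / (0.95 × 0.97 + 0.15 × 0.03) = 99.51%, as stated.

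Sample size on the logit scale: n = (z_a + z_b)² × [(Se/(1 − Se))/p + ((1 − Sp)/Sp)/(1 − p)] / [logit(NPV) − logit(0.984)]². With one-sided 5% and 85% power this is 7.189 × 188.94 / 1.2029² = 938.8. Dividing by 0.95 for the high-risk share gives 988.2, matching the stated 988. (A two-sided 5% level gives 1,234 and does not match.)

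The 85% and 95% therefore act as the accuracy of the questionnaire against a reference without error, although both documents label them as the kit's. The calculation contains no allowance for skin-test error.

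**Step 2: how many positives the bound allows.** About 1,000 × 0.95 = 950 are tested, 475 per group, if every low-risk subject completes testing. For n = 950 the two-sided exact lower bound is 98.49% with 7 positives and 98.35% with 8. At most 7 positives meet the target.

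**Step 3: add false positives in PST only.** Take true reactivity t = 1 − 0.9951 = 0.49% in both groups. The positive rate is t + (1 − t) × FP in PST and t in DOC. The chance of 7 or fewer positives comes from the sum of two independent binomials of size 475.

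| FP rate in PST | Expected positives | Expected pooled NPV | Chance bound is met |
|---|---|---|---|
| 0 | 4.7 | 99.51% | 90% |
| 0.5% | 7.0 | 99.26% | 60% |
| 1.0% | 9.4 | 99.01% | 28% |
| 1.7% | 12.7 | 98.66% | 6% |
| 5% | 28.3 | 97.02% | about 0 |

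With a one-sided 95% bound, 8 positives are allowed, and the chance is 95% with no false positives and 11% at 1.7%.

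**Step 4: limiting case, no true reactivity.** At FP 1.7% the expected count is 475 × 0.017 = 8.1 and the chance is 44% (two-sided) or 58% (one-sided). At 5% the expected count is 23.8 and the chance is about 0.

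**Step 5: PST alone, t = 0.49%.** Expected NPV is 97.82% at FP 1.7% and 94.54% at 5%. A single group of 475 allows only 2 positives, so even with no false positives the chance of a 98.4% bound is 59%.

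**The case against.** A reader might infer that the 98.4% bound cannot be reached. That holds at a 5% false-positive rate. At 1.7% success is unlikely rather than impossible, and with no true reactivity it is close to even.

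A reader might also take the 95% as the plan's own skin-test specificity and conclude that most positives are false. Step 1 shows that it works in the formula as the questionnaire's specificity. It also conflicts with the 1.7%: if only 1.7% of people without a history react, specificity in that population is at least 98.3%. Nor does Protocol 2.1 call those reactors false positives, and some may be truly sensitised. The documents thus give no settled false-positive rate, which is why a range is shown.

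It is tempting to note that 1 − 0.017 = 98.3% already lies below 98.4%. That sets a point value in people without a history against a confidence bound in low-risk people with one, and ignores DOC, the half that is never skin tested. Pooled with no true reactivity, 1.7% in PST gives an NPV of about 99.15%.

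The 3% prevalence scenario does not isolate the problem. If 3% of tested low-risk subjects truly react, the NPV is 97.0% and the bound fails without any false positive.

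The prevalence outcome is already worded as reactivity, so the wording point concerns the NPV only. SAP 7.4.1, 7.5 and 7.6 tabulate skin-test and challenge results, so the source of positives will be partly visible.

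The strongest objection concerns direction. Observation lasts 60 minutes in PST and 30 minutes after each dose in DOC (Protocol 6.3.1, 6.3.2), with no follow-up visits required (Protocol 6.4). Protocol 2.2.3 cites 806 direct challenges with 2 acute and 9 delayed reactions. Missed delayed reactions raise the NPV, so a claim that the overall NPV is biased down is not supported.

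What stands is that PST positives are never confirmed, and no analysis or power statement allows for that.

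**Conclusion.** The concern holds as a should-fix point. The stated 85% power for a 98.4% bound depends on a skin test with no false positives, an assumption the documents do not state. With 475 tested per group and 0.49% true reactivity, a two-sided exact bound is met with a chance of about 90% under that assumption, 60% at a 0.5% false-positive rate, 28% at 1.0%, 6% at 1.7% and about 0 at 5%.

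These figures assume that the challenge itself makes no errors and that all low-risk subjects are tested. With 380 per group (four sites of 200, as the Protocol Summary would imply, less 5%) the pattern is the same: 83%, 6% and about 0 at false-positive rates of 0, 1.7% and 5%. The downward effect is shown for the skin-test component only.

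**What to change.** 1. **SAP 7.3, reporting.** Give the NPV separately for PST and DOC as well as pooled. Describe the uncorrected PST result as an NPV for reactivity, not for true allergy. Group results will have wide intervals (Step 5), so treat them as descriptive.
2. **SAP 7.3, sensitivity analysis in both directions.** For PST, if the challenge finds everyone the skin test misses, observed positivity is p × Sp + (1 − Sp), so corrected prevalence is (observed − (1 − Sp))/Sp. Report it over a stated range, for example Sp = 95%, 98.3% and 100%, truncated at 0, with the interval limits transformed the same way. Add an assumed share of missed delayed reactions in both groups. Keep the uncorrected NPV as primary and do not apply the 98.4% bound to the corrected one: at Sp = 95% the formula goes negative whenever PST positivity is below 5%, so an assumed specificity could by itself produce success.
3. **SAP 7.3, short questionnaire.** Repeat the 4-6 question selection with skin-test-only positives left out, and report which questions survive.
4. **Protocol 8.2 and SAP 6.** State whether 85%/95% describes the questionnaire or the kit. The background separately says "the current kits are estimated to have a sensitivity of about 75" per cent, so the kit reading also needs reconciling on sensitivity. State that the 85% power assumes no skin-test false positives, and give the power over the range above.

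The cost is SAP wording and a few lines of code, with no new data, patients or procedures. The corrected figures rest on assumed error rates, must be shown as a range, and have wider intervals.
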